9.1.1 Study-Specific Clinical Outcomes

A list of anticipated AEs (AAEs) that are expected from underlying disease states are listed in Annex A of protocol – “*Clinical manifestations and medical occurrences, unintended diseases or injuries or clinical signs that are attributed to the concurrent illness / clinical condition of critically ill subjects in an ICU include*”.

All AEs that are listed under the above mentioned section of Annex A will be classified as “*study-specific clinical outcomes*”, as these AE(s) are by their nature, incidence, severity, and outcome previously identified in the risk analysis report and the State-of-the-Art analysis.

Study-specific clinical outcomes of patients in need of mechanical ventilation will be recorded in eCRF as secondary outcomes and **will not be recorded** as AEs **unless** the investigator deems the AE to be possibly, probably or definitely (causal) related to the mechanical ventilation itself (or lead to permanent discontinuation of study interventions (except death events that are considered as study specific clinical outcomes)), in which case such events would be recorded as (AEs).

The following AE(s) will be considered study-specific clinical outcomes:

1. Death related to the underlying illness or associated conditions based on the interpretation of the investigator.
2. Significant hemodynamic instability, defined as (a) norepinephrine-equivalent vasopressor dose initiation or increase from any dose that is both double and at least 0.15 mcg/kg/min increased over ≤ 60 minutes to maintain blood pressure target OR (b) dobutamine-equivalent inotropic dose initiation or increase from any dose that is both double and at least 5 mcg/kg/min over ≤ 60 minutes to maintain cardiac output target in case of left or right ventricular dysfunction/failure) that is related to the underlying illness or associated conditions based on the interpretation of the investigator
3. Progression of respiratory failure as demonstrated by new post-enrollment use of respiratory rescue therapy (e.g. ECMO, ECCO₂R, inhaled vasodilators, prone positioning), that is related to progression of the underling illness or associated conditions based on the interpretation of the investigator.
4. Anoxic brain injury that is related to the underling illness or associated conditions based on the interpretation of the investigator

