9.1.3 Serious Adverse Event (SAE)

ISO 14155 / MDR 2017/745 Definition (regulatory definition):

An SAE is any adverse event that led to any of the following:

- a) *led to a death*
- b) *led to a serious deterioration in health of the subject, users or other persons as defined by one or more of that resulted in any of the following:*
 - *a life-threatening illness or injury, or*
 - *a permanent impairment of a body structure or a body function, including chronic diseases, or*
 - *in-subject hospitalization or prolongation of existing patient hospitalization, or*
 - *in medical or surgical intervention to prevent life threatening illness or injury or permanent impairment to a body structure or a body function,*
 - *Chronic disease,*
 - *led to foetal distress, foetal death or a congenital abnormality or birth defect including physical or mental impairment physical or mental impairment or birth defect.*

Specificities to EASiVENT:

SAE recording begins after the patient has signed informed consent and has received INTELLiVENT-ASV or standard of care mechanical ventilation (point of enrollment). If a patient experiences a SAE after signing informed consent, but prior to receiving the study intervention, the event will not be recorded unless the investigator feels the event may have been caused by a study procedure.

SAEs will be collected Day 0 through Day 28 of the study period or until extubation, whichever occurs first. Thereafter, SAEs are not required to be recorded unless the investigator feels the events were possibly, probably, or definitely (causal) related to study procedures.

An SAE is any Adverse Event (AE) that results in one of the following events and is not classified as a study-specific clinical outcome using the definitions enumerated above:

1. Death that is not related to the underlying illness or associated condition or death that is possibly, probably, or definitely (causal) related to study procedures
2. Resuscitated cardiac arrest that is not related to the underlying illness or associated condition, or that is possibly, probably, or definitely (causal) related to study procedures

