3. Significant hemodynamic instability defined as (a) norepinephrine-equivalent vasopressor dose initiation or increase from any dose that is both double and at least 0.15 mcg/kg/min increased over > 60 minutes to maintain blood pressure target OR (b) dobutamin-equivalent inotropic dose initiation or increase from any dose that is both double and at least 5 mcg/kg/min over > 60 minutes to maintain cardiac output target in case of right ventricular dysfunction/failure, that is not related to the underlying illness or associated condition or that is possibly, probably, or definitely (causal) related to study procedures

4. Gross barotrauma (pneumothorax, pneumomediastinum, or subcutaneous emphysema) requiring chest tube or other surgical intervention, where the apparent barotrauma is not related to a procedural complication (e.g., a central venous catheter insertion causing pleural injury)
5. Significant hypercapnic acidemia ($\text{PaCO}_2 > 60 \text{ mm Hg}$ and $\text{pH} < 7.20$ with $\text{Vt} > 8 \text{ ml/kg PBW}$ and $\text{RR} > 30 \text{ b/min}$) for at least two consecutive arterial blood gas measurements 60 min apart
6. Significant hypocapnic alkalemia ($\text{PaCO}_2 < 30 \text{ mm Hg}$ with $\text{pH} > 7.50$) for at least two consecutive arterial blood gas 60 min apart
7. Significant hypoxemia (oxygen saturation < 85% or $\text{PaO}_2 < 55 \text{ mm Hg}$ with $\text{FiO}_2 1.0$) sustained for at least 30 minutes for at least two consecutive arterial blood gas measurements 60 min apart
8. Progression of respiratory failure as demonstrated by new post-enrollment use of respiratory rescue therapy (e.g. ECMO and ECCO₂R), if it is considered as related (possibly, probably, definitely (causal)) to the ventilation mode and neither to the underlying illness nor associated conditions based on the interpretation of the investigator.
9. Hypoxic brain injury, which must be documented with a confirmatory neuroimaging and other clinical evaluations as per local routine practice as applicable, a documented significant hypoxemia event (defined above) during study participation, that is not related to the underlying illness or associated condition
10. Other imminently life-threatening event that is not related to the underlying illness or associated condition or that is possibly, probably, or definitely (causal) related to study procedures

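### The outcome and SAE definitions of haemodynamic instability use opposite time windows as well as opposite attribution, so a ventilation-related dose rise over ≤60 minutes meets neither item and can drop out of the SAE count

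*Protocol*

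**What the plan says.** Protocol 9.1.1 (Study-Specific Clinical Outcomes), item 2, covers significant haemodynamic instability. Its vasopressor limb needs a norepinephrine-equivalent start or rise that is "both double and at least 0.15 mcg/kg/min increased over ≤ 60 minutes to maintain blood pressure target". Its inotrope limb uses the same ≤60-minute window, with a threshold of double and at least 5 mcg/kg/min, for "left or right ventricular dysfunction/failure) that is related to the underlying illness or associated conditions based on the interpretation of the investigator".

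Protocol 9.1.3 (Serious Adverse Event), item 3, names the same event with the same thresholds. Its vasopressor limb needs initiation or an "increase from any dose that is both double and at least 0.15 mcg/kg/min increased over > 60 minutes to maintain blood pressure target". Its inotrope limb needs a rise of "at least 5 mcg/kg/min over > 60 minutes to maintain cardiac output target" and applies "in case of right ventricular dysfunction/failure, that is not related to the underlying illness or associated condition or that is possibly, probably, or definitely" related to study procedures.

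The lead-in to the SAE list in 9.1.3 admits an event only if it "is not classified as a study-specific clinical outcome using the definitions enumerated above". Section 9.1.1 adds that an event on the outcome side is recorded as an AE after all if the investigator considers it at least possibly related to mechanical ventilation.

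Protocol 5.2 and SAP 3.2.2 and 8.3 make the number of SAEs within 28 days part of the secondary safety endpoint.

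**The concern.** The two lists appear meant to sort one event by cause. Death is handled that way: 9.1.1 item 1 and 9.1.3 item 1 differ by attribution alone. For haemodynamic instability the lists also differ by the speed of the dose rise and by the ventricle involved, and neither document gives a reason. When two definitions that should be complementary differ on more than one axis, some events fall between them.

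The events at stake are foreseeable. Annex A lists impaired right-ventricular loading from high plateau pressure and PEEP among the complications of ventilation. It also lists excessive PEEP and controller dysfunction among the anticipated effects of this device. The trial is pivotal and is intended to support a pre-market approval, so the SAE count will be read as evidence on device safety. A site that checks a rapid, ventilation-related rise against the only quantitative haemodynamic criterion in the SAE list would find that criterion not met.

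**Working it through.** No sample size, power or alpha figure is involved. The check sets the two items side by side and cross-classifies events.

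**Step 1: compare the definitions.**

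| Feature | 9.1.1 item 2 (outcome) | 9.1.3 item 3 (SAE) |
|---|---|---|
| Vasopressor threshold | double and ≥0.15 mcg/kg/min | same |
| Inotrope threshold | double and ≥5 mcg/kg/min | same |
| Time window, both limbs | ≤60 min | >60 min |
| Ventricular scope, inotrope limb | left or right | right only |
| Attribution | underlying illness or associated conditions | not the illness, or at least possibly study procedures |

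**Step 2: cross-classify the vasopressor limb (2 windows × 2 attributions = 4 cells).**

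| | Illness-related | Ventilation- or procedure-related |
|---|---|---|
| ≤60 min | outcome, item 2 | neither item |
| >60 min | neither item | SAE, item 3 |

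Two of the four cells are empty.

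**Step 3: add ventricular scope for the inotrope limb (4 × 2 = 8 cells).** Item 2 covers two cells (≤60 min, illness-related, left or right). Item 3 covers one (>60 min, not illness or procedure-related, right). That leaves 8 − 3 = 5 cells under neither item, including a ventilation-related rise over >60 minutes for left ventricular failure.

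**Step 4: look for other routes for the cell with ≤60 min and ventilation-related.**
- Recording: 9.1.1 and 9.1.2 item 2 both require a ventilation-related event to be recorded as an AE.
- SAE status through another listed item in 9.1.3, none with a time window on the dose rise: death (item 1), resuscitated arrest (item 2), the catch-all for other imminently life-threatening events (item 10), or a change of allocated mode judged related to that mode (item 11).
- SAE status through the regulatory definition at the start of 9.1.3, which includes intervention to prevent life-threatening illness and has no time window.

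What remains is a ventilation-related rise over ≤60 minutes that meets the dose threshold, leads to none of those events, and is not judged imminently life-threatening. It can be recorded as a non-serious AE and so not be counted as an SAE.

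**Step 5: the cell with >60 min and illness-related.** This meets neither numbered item. However, 9.1.1 also makes the Annex A list of illness-related events study-specific outcomes. That list includes sepsis, right and left heart failure, and other single- or multi-organ failure, so many such events have a place there.

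**Step 6: reporting time.** Table 4 gives SAEs and all ADEs the same limit of three calendar days. Section 9.2.2 defines an ADE by its relation to the device, and its Note 3 extends this to a comparator that is a medical device. The limit is therefore in doubt only for events judged related to ventilation but not to the device. If recorded as non-serious, these fall under the row for all other AEs, which has no fixed number of days.

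**The case against.** A reader might infer that an abrupt ventilation-related collapse escapes the SAE definition altogether, or is absorbed as a study outcome. The documents support neither. Item 2 of 9.1.1 requires attribution to the illness, so a ventilation-related event is not an outcome. A true collapse can qualify through items 1, 2, 10 or 11 of 9.1.3 or the regulatory definition. A reader might also infer that expedited reporting is lost in general; Table 4 rules that out for device-related events.

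The strongest case against acting is that central review closes the gap. Protocol 9.3 has events screened twice a day, assessed by the medical monitor and DSMB, and classified under the MDR and ISO 14155 definitions. AEs are also tabulated with severity (SAP 8.3 and 8.5). This narrows the practical loss, and it stands as mitigation. It does not settle the site's own entry: the study-specific part of 9.1.3 states what an SAE is in this trial and gives a numerical haemodynamic criterion. Two sites could classify the same event differently and both claim to follow the protocol.

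A second objection is that >60 minutes may mean a need sustained for that long. Neighbouring items 5 to 7 of 9.1.3 use persistence criteria with measurements 60 minutes apart. On that reading, an abrupt rise with prolonged support would meet item 3. The reading is possible, but the vasopressor limbs of both items describe the dose as increased over the stated interval, and nothing marks a change of meaning between them. If duration was intended, the wording still needs correcting.

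**Conclusion.** The inconsistency is real, and the SAE item is wrong as written. The two items should differ only by attribution; they also differ by time window in both limbs and by ventricular scope in the inotrope limb. Under these items, two of four vasopressor cells and five of eight inotrope cells are uncovered.

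The consequence is bounded. It concerns ventilation- or procedure-related events that meet the dose threshold and enter by no other SAE route. It affects the secondary SAE count and, for ventilation-related events not attributed to the device, the reporting clock. The co-primary endpoints are untouched. The documents give no frequency, so the number of events lost cannot be estimated; it could be none.

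The conclusion assumes that 60 minutes describes the speed of the dose rise, as the text reads, and that sites apply the study-specific SAE list. Annex D, the list of AEs to be recorded, is included by reference only and could not be checked for further guidance.

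**What to change.** Reconcile Protocol 9.1.1 item 2 and 9.1.3 item 3 so that both limbs use the same time window and the same ventricular criteria and the items differ only in attribution. State in both whether 60 minutes is the speed of the dose rise or the time for which it is sustained. The sponsor, medical monitor and DSMB must decide which window and scope apply; the documents do not settle it. Align the eCRF guidance, and Annex D if it repeats the definition.

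The cost is wording in section 9 and the eCRF guidance. Sample size, co-primary analyses and visit schedule do not change. If haemodynamic events have already been classified under the present wording, re-read them in both arms under the agreed one, so that the SAE count rests on a single definition.

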8.3.1 General management in both groups

From inclusion up to day of extubation (and not reintubated within 48h after extubation), ventilation settings will be adjusted by the attending physician or respiratory therapist. Subject condition, sedation, analgesic and vasopressor use, and one blood gas analysis will be collected twice a day if blood gas analysis is done routinely by the ICU department, otherwise ventilation parameters will only be collected.

Subjects will be monitored by the attending physicians and all ventilation variables will be continuously recorded from inclusion to extubation or death. Except for ventilation, all other procedures and care (sedation, hemodynamics, glycemic control, etc.) will be conducted according to the protocols of the site by the subject's attending physicians.

Data listed below will be captured in the eCRF:

- Intubation/reintubation status
- INTELLIVENT-ASV randomization violation status
- Vitals signs: Blood pressure, pulse rate and temperature;
- Acute pulmonary condition;
- 24h Recording of ventilation parameters (Memory Box)

- Ventilation settings
- All concomitant medications including sedation;
- SOFA will be repeated at day 3 and 7, in order to follow the evolution of organ failure.
- Memory Box recording
- Blood gas analysis
- Severity scores based on the most abnormal values in oxygenation and laboratory results in the last 24h period (day 0):
 - Simplified Acute Physiology Score (SAPS II)
 - Acute Physiology and Chronic Health Evaluation (APACHE II)
 - SOFA score
- Concomitant sedation, analgesia and myorelaxants use
- Concomitant vasopressors and inotropics use
- Number of recruitment movers within the last observation period
- Concomitant rescue therapies (proning, Nitric oxyde, ...)
- Weaning information associated interventions (Patient Passive/Active but still on MV, NIV, CPAP, High Flow.)
- Advers Event collection

Recorded data has to be 24 hours at minimum and 80% of the invasive ventilation duration within the allocated randomized ventilation mode have to be recorded in the in Memory Box.

If the subject's medical condition requires medical intervention (bronchoscopy, trancescopy, radiology or OR interventions...etc) and the subject is allocated to the INTELLiVENT-ASV arm, the allocated randomized ventilation mode may be switched off for the required time period. This needs to be documented in the subject's medical chart.

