Dropout could occur when patients are ventilated for less than 24 hours after inclusion because of unexpected death, transfer to another ICU, or withdrawal of informed consent. We expect a maximum of 5% of these cases. Note a maximum of 5% of subjects are anticipated for which not 80% of mechanical ventilation time could be recorded within the allocated randomized ventilation mode due to documented technical reason. The recorded data will be used (with 'percent spent' calculated per the recorded time) for the primary analysis of the co-primary endpoints. As a sensitivity analysis, these values will be treated as missing data.

If the ventilation mode is modified by the site personnel by oversight or lack of training (deviating from the allocated randomization arm) and the subject's medical condition did not require it, the ventilation mode should be set back to allocated randomization arm. A protocol deviation and the event will be recorded in the eCRF accordingly.

If the site's principal investigator determines that the study is no longer in the subject's best interest (including the randomized ventilation mode) the subject's ventilation and study data collection ends. The site needs to complete an AE and the End of Study eCRF.

A. Gas exchanges targets:

SpO₂ will be kept in the ranges:

- 94 - 98% for normal lung, mild and moderate ARDS, and brain injured subjects
- 90-96% for moderate ARDS
- 88 - 95% for severe ARDS
- 90 - 94% for COPD without chronic hypoxemia or hypercapnia
- 88 - 92% for chronic hypercapnic subjects or subjects on long term oxygen

PaCO₂ will be kept in the range:

- 35 - 40 mm Hg for brain injury
- 35 - 50 mm Hg for normal lung, mild and moderate ARDS, COPD subjects without chronic hypercapnia
- ≥ 50 mm Hg in severe ARDS, severe COPD, and subjects with chronic hypercapnia if pH > 7.25

B. Passive subjects:

i. Ventilator settings:

Tidal volume will be kept in the range:

- 6-10 mL/Kg IBW for normal lung subjects, brain injury, and COPD subjects
- 4-8 mL/Kg IBW for ARDS

ii. Lung protection monitoring:

Plateau pressure will be measured at least twice a day and kept below 30 cmH₂O. Driving pressure will be measured at least four times a day and kept below 15 cmH₂O in all subjects.

In ARDS subjects, Plateau pressure between 30 and 35 cmH₂O will be accepted if driving pressure remains below 15 cmH₂O.

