8.3.2 Ventilation protocol in non-automated ventilation group

In order to standardize the non-automated ventilation process, Investigators will aim to keep the control arm (conventional non-automated ventilator) as close to the standard of care of the participating sites as possible.

General approach: The overall goals for the control arm ventilation protocol will be similar to those in the INTELLIVENT-ASV group including all recommendation available regarding gas exchanges targets, ventilator settings, protective ventilation targets, and weaning management (16, 32).

A. Passive subjects:

i. Ventilation mode

Any controlled mode will be possible such as volume control (CMV), pressure control (P-CMV), dual mode (APVcmv and APVsimmv), DuoPAP, SIMV, and P-SIMV. APRV will not be accepted. Tube resistance compensation (TRC) can be added.

ii. Ventilator settings

Respiratory rate will be adjusted according to PaCO_2 with a maximum of 35 Breaths/min.

Table 2: Management of pH and PaCO_2 :

$\text{pH} < 7.15$	$\text{pH}= 7.15 - 7.29$	$\text{pH}= 7.29 - 7.45$	$\text{pH} > 7.45$
Increase Respiratory rate up to 35 b/min and keep $\text{PaCO}_2 > 25$ mm Hg	Increase Respiratory rate up to 35 b/min and keep $\text{PaCO}_2 > 25$ mm Hg	Maintain VT around 6 mL/kg IBW in ARDS subjects and between 6 – 8 mL/Kg IBW for other subjects and maintain respiratory rate below 35 b/min.	Decrease respiratory rate but not below 6 /min
Consider NaHCO_3 If needed increase VT by 1 ml/Kg IBW or increase P_{INSP} by 2 cmH ₂ O with a maximum VT at 8 mL/Kg IBW for ARDS subjects and 10 mL/Kg IBW for other subjects. P_{PLAT} can be higher than 35 cmH ₂ O in case of extreme acidosis.	Consider NaHCO_3 If needed increase VT by 1 ml/Kg IBW or increase P_{INSP} by 2 cmH ₂ O with a maximum VT at 8 mL/Kg IBW for ARDS subjects and 10 mL/Kg IBW for other subjects. Keep $P_{\text{PLAT}} \leq 35$ cmH ₂ O.	Consider NaHCO_3 If needed increase VT by 1 ml/Kg IBW or increase P_{INSP} by 2 cmH ₂ O with a maximum VT at 8 mL/Kg IBW for ARDS subjects and 10 mL/Kg IBW for other subjects. Keep $P_{\text{PLAT}} \leq 35$ cmH ₂ O.	Consider NaHCO_3 If needed decrease VT by 1 ml/Kg IBW or decrease P_{INSP} by 2 cmH ₂ O with a minimum VT at 4 mL/Kg IBW for ARDS subjects and 5 mL/Kg IBW for other subjects.

PEEP will be set using PEEP/FiO₂ table, PEEP trial or transpulmonary pressure (based on the local hospital protocol).

PEEP will be kept in the range:

- 5-10 cmH₂O for normal lung subjects and COPD

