By the nature of this patient population a myriad of **non-serious Adverse Events (AEs)** will occur during the Study. Due to the complexity of critical illness, it may be difficult for the investigators to classify whether an Adverse Event (AE) is related or not to the underlying condition or the sequelae of it or to mechanical ventilator support.

Therefore, investigators will be instructed that events such as:

- a. transitory hypertension or
- b. hypotension, tachy- or bradycardia,
- c. arrhythmias (such as atrial fibrillation, heart block, ventricular tachycardia, or ventricular fibrillation),
- d. transitory hypoxemia or
- e. hypercapnia,
- f. impaired cognitive function due to sedation/analgesia or delirium (see AE list attached),

Are not considered study population specific clinical outcomes and **should be recorded** as adverse events **only** if they are **serious** events **or are considered to be related to mechanical ventilation or lead to discontinuation of INTELLiVENT-ASV mode.**

The blinded medical monitor and DSMB will evaluate investigator-reported SAEs and AEs and independently assess potential relatedness to study procedures and, where indicated, make recommendations for safety modifications to the protocol, temporary suspension, or even termination of the study.

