Asia-Pacific	577
Europe	2190
Indian Subcontinent	24
Latin America	267
The Middle East and Africa (MEA)	518
Total	3576

Until now, there has been no reported problems, events, serious adverse events or recalls due to the INTELLiVENT-ASV accessory software on HAMILTON ventilators. The vigilance database searches for Bfarm (the German database and the largest European database for medical device adverse event

reporting) did not yield any events, reported problems, serious adverse events due to or related to INTELLiVENT-ASV.

Anticipated device deficiencies from risk management activities of the manufacturer:

Anticipated Serious adverse device effect which by its nature, incidence, severity or outcome has been identified in the current version of the risk analysis report

- User errors such as false settings, wrong subject's conditions and offset setting
- Delayed detection of the change of the status of the subject
- Incorrect SpO₂ measurement
- Incorrect CO₂ measurement
- Too low signal quality
- Wrong sensor values
- Subject ventilated with the wrong target range
- PEEP too high
- Controller dysfunction
- Target shifts for SpO₂ or FiO₂
- Too early extubation based on only ventilatory parameters
- User thinks he is in automatic mode but is in manual mode
- controller dysfunction
- Trigger too sensitive leading to false (auto) triggering

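### SAE item 5 counts hypercapnic acidemia only with tidal volume above 8 mL/kg and rate above 30/min, so ARDS subjects within the protocol's range, and under-ventilated subjects of any kind, cannot meet it

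*Protocol*

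**What the plan says.** Protocol section 9.1.3, item 5 lists "Significant hypercapnic acidemia" among the events that make an SAE. Four conditions must hold together: PaCO2 above 60 mm Hg, pH below 7.20, tidal volume above 8 mL/kg PBW, and respiratory rate above 30/min. They must hold "for at least two consecutive arterial blood gas measurements 60 min apart". The next item, hypocapnic alkalemia, uses PaCO2, pH and a repeat gas only.

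The section titled "8.3.1 General management in both groups" gives the tidal-volume range as "4-8 mL/Kg IBW for ARDS", once for passive and once for spontaneously breathing subjects. Table 2 in section 8.3.2 (control arm) allows tidal volume to be raised in acidosis, "with a maximum VT at 8 mL/Kg IBW for ARDS subjects and 10 mL/Kg IBW for other subjects". This wording also stands in the column for pH below 7.15. Section 8.3.3 states no tidal-volume limit of its own for the INTELLiVENT-ASV arm.

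Section 9.1.2 says that events such as hypercapnia are recorded as adverse events only if they are serious, are considered related to mechanical ventilation, or "lead to discontinuation of INTELLiVENT-ASV mode". The number of SAEs within 28 days is part of the secondary safety endpoint (protocol 5.2, SAP 8.3).

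**The concern.** The device is a closed-loop controller of CO2 elimination. A sustained rise in arterial CO2 with acidosis is one of the main harms that such a controller could cause. Annex A lists "Incorrect CO₂ measurement", wrong sensor values and controller dysfunction among the anticipated problems, and the direct result of such faults can be too little delivered ventilation. Item 5 is the only SAE item that names this harm with an objective blood-gas threshold and no relatedness clause. Its two ventilator conditions exclude the low-ventilation form of the event. They also exclude every ARDS subject kept within the protocol's own range.

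The trial is pivotal and is meant to support a premarket approval application. A low or zero count under item 5 could be read as showing safe CO2 control when many of the relevant cases could not have qualified.

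**Working it through.** The documents state no figure to reproduce. The check is whether the item 5 region overlaps the ventilation ranges that the protocol allows.

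**Inputs**
- Item 5 (9.1.3): VT > 8 mL/kg PBW and RR > 30/min.
- ARDS, both arms (8.3.1 B and C): VT 4-8 mL/kg IBW.
- Other conditions (8.3.1): VT 6-10 mL/kg IBW.
- Rate ceiling: 35/min for spontaneous breathing (8.3.1 C) and for passive control subjects (8.3.2).

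**Overlap**

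| Group | Allowed VT | Allowed RR | Part that meets item 5 |
|---|---|---|---|
| ARDS | 4 to 8 | up to 35 | none |
| Other conditions | 6 to 10 | up to 35 | VT above 8 to 10 with RR above 30 to 35 |

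At the ARDS ceiling (VT 8.0, RR 35) the strict inequality VT > 8 still fails.

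**Minute ventilation implied by item 5**
- Lower bound: 8 × 30 = 240 mL/kg/min. For illustrative weights this is 14.4 L/min at 60 kg and 16.8 L/min at 70 kg.
- ARDS subject at the ceiling: 8 × 35 = 280 mL/kg/min. This exceeds 240, yet the subject does not qualify.
- So item 5 does not work as a definition of acidemia despite high support either. Acidemia with VT at or below 8, or RR at or below 30, fails in every lung condition.

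**Comparison with Table 6**
- Passive ARDS: VT above 8 to 10 is graded acceptable.
- Active ARDS: VT 5 to 10 is graded optimal.
- These are endpoint grades, not management rules, but they do not match the 4-8 range in 8.3.1. Item 5 also uses PBW where the ranges use IBW, and the documents do not say whether the two are the same.

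**Subjects affected under the ARDS limb**

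The trial's ARDS share is not given. Annex A offers 3% (Table 9, root cause of ventilation), 10% (Table 10, at ICU admission) and 24% (Table 10, all ventilated subjects).
- 254 subjects: 0.03 × 254 = 7.6; 0.10 × 254 = 25.4; 0.24 × 254 = 61.0.
- 508 subjects: 0.03 × 508 = 15.2; 0.10 × 508 = 50.8; 0.24 × 508 = 121.9.

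These count subjects who could not register the event while within range. They are not missed events, because the documents give no incidence of PaCO2 above 60 with pH below 7.20.

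**The case against.** A reader might infer that all device-caused CO2 failure drops out of safety reporting. The documents do not support that. Item 11 makes a change of allocated mode an SAE if it is judged related to the mode, with no volume or rate condition. Item 8 covers rescue therapy judged related to the mode, and item 10 covers imminently life-threatening events. The general ISO definition of seriousness precedes the list. Related non-serious AEs are recorded (9.1.2), and device deficiencies are reported under 9.2. The medical monitor and DSMB review AEs as well as SAEs and assess relatedness themselves. The co-primary safety endpoint also grades PetCO2 with no volume or rate condition; above 52 mm Hg is sub-optimal in passive ARDS.

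This stands, with limits:
- Items 8 and 11, and the related-AE route, depend on judgement by investigators who know the arm (6.2.2).
- Item 11 needs a mode change. Table 3 responds to pH below 7.15 by lowering the PetCO2 target, which is not one.
- A non-serious AE or a device deficiency does not enter the SAE count.
- PetCO2 grading fails as a check when the CO2 sensor itself misreads.

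A second tempting reading is that no ARDS subject can ever meet item 5. That is also too strong. A subject whose volume drifts above 8 mL/kg could qualify, the device-arm limit rests on 8.3.1 alone, and Table 6 treats volumes above 8 as acceptable or optimal.

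Finally, a condition on support level may be deliberate: item 7 (hypoxemia) refers to FiO2 1.0. Excluding tolerated hypercapnia would not explain it, since 8.3.1 accepts PaCO2 of 50 or more in severe ARDS, severe COPD and chronic hypercapnia only if pH is above 7.25. The documents give no reason for the volume and rate conditions. The AE list in Annex D is by reference only, so how it treats hypercapnia cannot be checked.

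**Conclusion.** The point holds for item 5 as written. An ARDS subject within the 8.3.1 range cannot meet it, nor can any subject whose acidemia comes with low delivered volume or rate. The SAE count can therefore miss such events unless another, mostly judgement-based, route makes them serious.

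The ARDS limb concerns about 8 to 61 of 254 subjects if the Annex A shares of 3% to 24% apply; quoting only the upper figure would be selective. The low-ventilation limb applies to every lung condition. The number of missed events cannot be estimated from the documents. The result assumes that PBW and IBW are equivalent and that care stays within 8.3.1. Severity: should-fix, because the definition is wrong for its purpose and cheap to change, while part of the gap is covered elsewhere.

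**What to change.** Reconcile item 5 with 8.3.1, Table 2 and Table 6, and state whether PBW and IBW are the same. Classify the event by its existing PaCO2, pH and persistence criteria, in the form that item 6 already uses, and record tidal volume and rate at the time as descriptors on the SAE form. This changes event classification only, not ventilation management; which ventilation limits are right is for the sponsor to settle.

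At a minimum, add a SAP table by arm of all recorded blood gases meeting item 5's existing PaCO2 and pH values, regardless of volume and rate. Limit any retrospective step to gases actually available: the eCRF takes them about twice a day and only if done routinely (8.3.1, 8.3.4), so pairs 60 minutes apart may be missing or need source records.

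The cost is a short protocol amendment and an eCRF check. Expect more SAE reports in both arms, including disease-driven acidemia, since item 5 has no clause excluding the underlying illness. Relatedness is already to be recorded for each event and can separate these.
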